#### 5.4.3 Other Efficacy Analyses

The score of EQ-5D-Y each items (Mobility, Looking after myself, Doing usual activities, Having pain or discomfort, Feeling worried, sad or unhappy) will be summarized for each visit using frequency count (number and percentage). The measurement and the change from baseline of EQ-5D-Y VAS at each visit will be summarized using descriptive statistics (n, mean, standard deviation, median, minimum and maximum).

### 5.5 Pharmacokinetic, Pharmacodynamic, Pharmacogenomic, and Other Biomarker Analyses

Perampanel plasma concentrations were obtained from blood samples drawn at any time during the treatment phase (Weeks 15, 19 and 23/EOT). Details of the analysis methods for population PK/PD modeling will not be described in this SAP but will be described in a separate analysis plan.

#### 5.5.1 Pharmacokinetic Analyses

Population PK analysis will be performed to characterize the PK of perampanel by pooling the concentration data with other studies, including 19 Phase 1 studies, 2 Phase 2 studies (232 and 235), and 5 Phase 3 studies (304, 305, 306, 332, and 335). A 2-compartment PK model will be fit to the data and the effect of intrinsic and extrinsic factors, including body weight and age, on the PK of perampanel will be evaluated. The post-hoc estimates of both

maximum observed concentration ( $C_{max}$ ) and area under the curve (AUC) from the final PK model will be derived for all subjects. In addition, average steady-state drug concentration ( $C_{ss,av}$ ) will be calculated. Subsequently, the dose-normalized derived exposure parameters will be summarized descriptively by age group ( $\leq 4$  years,  $>4$  to  $\leq 8$  years,  $>8$  to  $<12$  years,  $\geq 12$  to  $<18$  years, and  $\geq 18$  years) for subjects with and without inducing AEDs, and also presented in box-plots.

### 5.5.2 Pharmacodynamic, Pharmacogenomic, and Other Biomarker Analyses

PD endpoints to be evaluated as part of PK/PD analyses include endpoints for efficacy, cognition, and selected safety parameters.

## 5.6 Safety Analyses

All safety analyses will be performed on the Safety Analysis Set (SAS). Safety data will be summarized on an “as treated” basis using descriptive statistics (eg, n, mean, standard deviation, median, minimum, maximum for continuous variables; n [%] for categorical variables). Safety variables include TEAEs, clinical laboratory parameters, vital signs, 12-lead ECG results, C-SSRS, growth parameters, CBCL and LGPT. Study Day 1 for all safety analyses will be defined as the date of the 1st dose of study drug.

### 5.6.1 Extent of Exposure

The duration of treatment (Titration Period and Maintenance Period of the Core Study) will be calculated as the number of weeks between the date the subject receives their 1st treatment dose and the date the subject receives the last dose of treatment. These values will be used to summarize the extent of exposure to study medication.

Modal dose, mean daily dose, maximum daily dose and last daily dose will be presented using summary statistics and frequency using categories of  $< 4$ ,  $4$ ,  $>4-<8$ ,  $8-<12$ ,  $12=\leq$ . Number and percent of subjects who down-titrated or discontinued study at maximum daily dose exposed will be summarized using frequency count (number and percentage).

### 5.6.2 Adverse Events

The AE verbatim descriptions (investigator terms from the CRF) will be classified into standardized medical terminology using the Medical Dictionary for Regulatory Activities (MedDRA). AEs will be coded to the MedDRA (version 18.1 or higher) lower level term closest to the verbatim term. The linked MedDRA PT and primary system organ class (SOC) are also captured in the database.

A TEAE is defined as an AE that emerges from the date of first dose of study drug to 28 days after last end date of dose in prescribed dose entry, having been absent at pretreatment (Baseline) or

- Reemerges during treatment, having been present at pretreatment (Baseline) but stopped before treatment, or

- Worsens in severity during treatment relative to the pretreatment state, when the AE is continuous.

Only those AEs that are treatment-emergent will be included in summary tables. All AEs, treatment-emergent or otherwise, will be presented in subject data listings.

The TEAEs will be summarized using the Safety Analysis Set. The incidence of TEAEs will be reported as the number (percentage) of subjects with TEAEs by SOC and PT. A subject will be counted only once within an SOC and PT, even if the subject experienced more than 1 TEAE within a specific SOC and PT. The number (percentage) of subjects with TEAEs will also be summarized by maximum severity (mild, moderate, or severe).

The number (percentage) of subjects with TEAEs will also be summarized by relationship to study drug (Yes [related] and No [not related]).

The number (percentage) of subjects with treatment-related TEAEs will be summarized by SOC and PT. Treatment-related TEAEs include those events considered by the investigator to be related to study treatment.

The number (percentage) of subjects with TEAEs leading to death will be summarized by MedDRA SOC and PT. A subject data listing of all AEs leading to death will be provided.

The number (percentage) of subjects with treatment-emergent SAEs will be summarized by MedDRA SOC and PT. A subject data listing of all SAEs will be provided.

The number (percentage) of subjects with TEAEs leading to discontinuation from study drug will be summarized by MedDRA SOC and PT. A subject data listing of all AEs leading to discontinuation from study drug will be provided.

An overview of TEAEs and the number (percentage) of subjects with TEAEs by speed of titration, 'Fast' and 'Other', will be summarized by MedDRA SOC and PT for safety set. 'Fast' titrators are defined as subjects who spent less time on any one dose prior to attaining their maximum dose than was permitted by the protocol and 'Other' is defined as all other subjects.

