9.1.2.1 Titration Period

During the Titration Period, subjects will be stratified by the presence or absence of concomitant EIAEDs and will be titrated using the dosing schedule based on individual clinical response and tolerability no more frequently than at weekly intervals, up to 8 mg/day for non-EIAED subjects or 12 mg/day for EIAED subjects. With the exception of subjects enrolled in Japan, EIAED subjects may titrate beyond 12 mg/day and up to 16 mg/day if they tolerate 12 mg/day and are deemed likely to benefit from a higher dose. Non-EIAED subjects may go beyond 8 mg/day and up to 12 mg/day if they tolerate 8 mg/day and are deemed likely to benefit from a higher dose. Subjects will be flexibly dosed based on individual tolerability. Regardless of EIAED status, subjects enrolled in Japan may not receive doses higher than 12 mg/day. The Titration Period is a duration of up to 11 weeks, during which multiple dose adjustments are allowed in order to identify each subject's optimum dose. All visits are to be done within ± 3 days of the schedule. Each study visit is based on the actual prior visit (eg, Visit 3 is completed 2 weeks ± 3 days of Visit 2, Visit 4 is completed 3 weeks ± 3 days of Visit 3, Visit 5 is completed 3 weeks ± 3 days of Visit 4). (revised per Amendment 02) Subjects will remain on their optimum dose once it is achieved during the Titration Period. (revised per Amendment 01) The dosing schedule is illustrated in [Table 1](#).

According to the investigator's clinical judgment, subjects experiencing intolerability at any dose may remain at the same dose or have their dose decreased 1 dose level down to the previously tolerated dose. If the subject continues to present significant intolerable AEs at the decreased dose and the investigator deems it is necessary, the dose can be decreased further to the next dose level down. Dose decreases can be done via telephone. Subjects whose dose has been decreased can have their dose increased again if tolerability improves; this can be done at the next clinic visit after the investigator has deemed it is appropriate in view of resolution of the AE(s). Multiple dose adjustments will be allowed during the Titration Period. Only upon completion of the 11 weeks Titration Period, subjects will enter the Maintenance Period. (revised per Amendment 01)

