9.4.1 Treatment(s) Administered

Core Study

Pretreatment Phase:

The Pretreatment Phase will consist of a Screening/Baseline Period that lasts up to 4 weeks \pm 3 days outside of Japan. Subjects in Japan are required to complete 4 full weeks \pm 3 days of the Screening/Baseline Period before they may enter the Treatment Phase (ie, Visit 2). However, subjects outside of Japan may begin treatment as soon as baseline procedures have been completed and documentation of eligibility (such as a documented seizure diary entry for a qualifying seizure during the preceding 12 weeks prior to Visit 2 or a qualifying seizure during the prospective Screening/Baseline Period) has been established. (revised per Amendment 02) During this phase, subjects will continue to take their baseline AEDs regimen as allowed per inclusion/exclusion criteria. No study drug will be administered to subjects during this phase.

Treatment Phase:

The treatment phase will consist of 3 periods: Titration (up to 11 weeks), Maintenance (up to 12 weeks), and Follow-up (up to 4 weeks; only for those subjects not rolling over into Extension A). (revised per Amendments 01, 02, and 03)

- ***Titration Period***

During the Titration Period, subjects will be stratified by the presence or absence of concomitant EIAEDs and will be titrated using the dosing schedule presented in [Table 1](#) (Global) and [Table 2](#) (Japan only) based on individual clinical response and tolerability no more frequently than at weekly intervals, up to 8 mg/day of perampanel for non-EIAED subjects or 12 mg/day for EIAED subjects. (revised per Amendment 01) EIAED subjects who are not enrolled in Japan may titrate beyond 12 mg/day and up to 16 mg/day if they tolerate 12 mg/day and are deemed likely to benefit from a higher dose. Subjects enrolled in Japan and receiving EIAEDs may not receive doses higher than 12 mg/day. Non-EIAED subjects may go beyond 8 mg/day and up to 12 mg/day if they tolerate 8 mg/day and are deemed likely to benefit from a higher dose. Subjects will be flexibly dosed based on individual tolerability. The Titration Period is a duration of up to 11 weeks during which multiple dose adjustments are allowed in order to identify each subject's optimum dose. (revised per Amendment 02) Subjects will remain on their optimum dose once it is achieved during the Titration Period. (revised per Amendment 01)

Table 1 Dosing Schedule (Global)

(revised per Amendment 01)

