Week	Subjects on Concomitant EIAEDs (mg/day)	Subjects NOT on Concomitant EIAEDs (mg/day)
0	4	2
1	6	4
2	8	6
3	10	6
4	10	8
5	12	8
6	12	10
7	14	10
8	14	12
9	16	12
10	16	—

EIAED = enzyme inducing antiepileptic drug.

For subjects not on concomitant EIAEDs, titration above 8 mg/day doses is contingent on subject tolerability.

Table 2 Dosing Schedule (Japan Only)

(revised per Amendment 01)

Week	Subjects on Concomitant EIAEDs (mg/day)	Subjects NOT on Concomitant EIAEDs (mg/day)
0	2	2
1	4	4
2	6	6
3	6	6
4	8	8
5	8	8
6	10	10
7	10	10
8	12	12
9	12	12
10	—	—

EIAED = enzyme inducing antiepileptic drug.

For subjects not on concomitant EIAEDs, titration above 8 mg/day doses is contingent on subject tolerability.

According to the investigator's clinical judgment, subjects experiencing intolerability at any dose may remain at the same dose or have their dose decreased 1 dose level down to the previously tolerated dose. If the subject continues to present significant intolerable AE(s) at the decreased dose and the investigator deems it is necessary, the dose can be decreased further to the next dose level down. Dose decreases can be done via telephone. Subjects whose dose has been decreased can have their dose increased again if tolerability improves; this can be done at the next clinic visit after the investigator has deemed it is appropriate in view of resolution of the AE(s). Multiple dose adjustments will be allowed during the Titration Period. Upon completion of the Titration Period, subjects will enter the Maintenance Period.

- ***Maintenance Period***

During the Maintenance Period of the Core Study (up to 12 week), subjects will continue taking perampanel oral suspension once daily at the dose level they achieved at the end of the Titration Period. Multiple dose adjustment is allowed if a subject is experiencing intolerable AE(s) or a higher dose is deemed to be beneficial. All visits are to be done within ± 7 days of the schedule. Each study visit is based on the actual prior visit (eg, Visit 6 is completed 3 weeks ± 7 days of Visit 5, Visit 7 is completed 4 weeks ± 7 days of Visit 6, Visit 8 is completed 4 weeks ± 7 days of Visit 7, Visit 9 is completed 4 weeks ± 7 days of Visit 8. (revised per Amendment 02)

During the Titration and Maintenance Periods, all dose adjustments will be done via 1 dose level up or down. Those who cannot tolerate a minimum of 2 mg dose must discontinue from the study.

Extension A

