## 7 CHANGES IN THE PLANNED ANALYSES

The following major changes to the statistical methods in this analysis plan were made after version 2.0 of the SAP was approved.

- The study design was updated with the changes from latest protocol (V9.0).
- Efficacy analysis of the percent change in seizure frequency of POS total seizure in the subgroups of patients receiving at least 6mg, in the completer population, by age of onset, by duration of disease (month) and by CNS concomitant medication (Yes / No) was deleted since the overall efficacy analysis was deemed sufficient. .
- EEG analysis was defined another document.
- Overview of TEAE and TEAEs SOC/PT by speed of titration were added .

Other changes were editorial in nature, to add clarification or maintain consistency with the latest Eisai SAP template.

Any future changes to the analysis will be documented separately and will be addressed in the Clinical Study Report.

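### The Core SAP's Fast/Other titration-speed table is confounded by how far each child escalated and rests on a time limit that can be read two ways; the direction of the distortion is unknown

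*SAP*

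**What the plan says.** Core SAP 5.6.2 plans an overview of TEAEs, and counts and percentages of children with TEAEs by system organ class and preferred term, in two groups. Fast children are "subjects who spent less time on any one dose prior to attaining their maximum dose than was permitted by the protocol". Other is the remainder. No number of days is given, and the definition does not say whether a short stay caused by a dose reduction counts.

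The same section counts TEAEs from the first dose to 28 days after the last. SAP Section 5 exempts this one summary from the breakdown by age, disease and inducer status. SAP Section 7 records its late arrival: "Overview of TEAE and TEAEs SOC/PT by speed of titration were added", after version 2.0 was approved.

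Protocol 9.4.1 says that children are "titrated using the dosing schedule presented in" Tables 1 and 2 and, in the same sentence, that increases come "no more frequently than at weekly intervals". Section 9.1.2.1 repeats the weekly cap. On tolerability, 9.4.1 says "subjects experiencing intolerability at any dose may remain at the same dose or have their dose decreased 1 dose level down", and a note under each table adds: "For subjects not on concomitant EIAEDs, titration above 8 mg/day doses is contingent on subject tolerability".

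**The concern.** The label is assigned after the fact, from a path that adverse events help to shape. A child whose escalation is ended by an event at the starting dose has no earlier hold to shorten and goes into Other by construction. A child who tolerates the drug has more holds, more chances of a short one, and more time at higher doses. Events that occur before any short hold still count against Fast. A raw difference between the columns therefore mixes speed with tolerability and with dose.

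The threshold adds a second problem. If the weekly cap and the printed schedules imply different minimum stays, two programmers following the SAP could produce different tables.

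Safety and tolerability is the primary objective, and this is the Core SAP's only planned look at escalation speed. A reader will be inclined to take the table as evidence on that question.

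**Working it through.** The documents give no expected Fast share, TEAE rate, power or alpha for this comparison, so there is no stated figure to reproduce. The rates below are assumptions.

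**1. The two limits.** Counting weeks per dose in Protocol 9.4.1:

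| Column | One-week doses | Two-week doses before the top | Top dose first reached: weekly steps / tables |
|---|---|---|---|
| Global, no EIAED; all Japan | 2, 4 mg | 6, 8, 10 mg | 12 mg at Week 5 / Week 8 |
| Global, EIAED | 4, 6, 8 mg | 10, 12, 14 mg | 16 mg at Week 6 / Week 9 |

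A child who holds one of the two-week doses for 7 to 13 days is Fast if the tables set the limit and Other if the weekly cap does.

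**2. Dependence on escalation.** Let q be the chance that any one hold is short and k the number of completed upward steps. Then P(Fast | k) = 1 - (1 - q)^k.

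| q | k=0 | k=1 | k=2 | k=3 | k=5 | k=6 |
|---|---|---|---|---|---|---|
| 0.1 | 0% | 10% | 19% | 27% | 41% | 47% |
| 0.2 | 0% | 20% | 36% | 49% | 67% | 74% |
| 0.3 | 0% | 30% | 51% | 66% | 83% | 88% |

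The full schedule has five steps, or six in the global EIAED column, so EIAED status also enters the label.

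**3. Two opposing forces when speed has no effect.**

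*Towards Fast looking safer.* Suppose a fraction s of children is stopped by an event at the starting dose and the rest complete k steps with TEAE risk r. Fast shows r. Other shows [s + (1-s)(1-q)^k r] / [s + (1-s)(1-q)^k], which exceeds r whenever s > 0 and r < 1.

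*Towards Fast looking worse.* Suppose no event stops escalation, half the children go to 8 mg (3 steps) and half to 12 mg (5 steps), and q = 0.2. The 12 mg share is 0.672/(0.672 + 0.488) = 0.579 among Fast and 0.328/(0.328 + 0.512) = 0.390 among Other. Fast minus Other is then 0.189 times the difference in TEAE risk between the 12 mg and 8 mg children: 1.9 points for every 10 points of difference.

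**4. Net effect on any TEAE.** Day-level simulation of the 2-to-12 mg schedule over 161 days, with 120,000 children per scenario and no effect of speed. Assumptions: q = 0.2; half aim for 12 mg and half for 8 mg; a short hold is 4 days on a one-week dose and 7 days on a two-week dose. In the first three rows, 30% of children carry a higher hazard.

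| An event stops escalation / ends treatment | Hazard | Fast minus Other, table limit | Fast minus Other, weekly limit |
|---|---|---|---|
| 70% / 30% | flat in dose | -7.9 | -2.8 |
| 60% / 20% | flat in dose | -6.3 | -2.4 |
| 25% / 10% | proportional to dose | +1.0 | +0.3 |
| 5% / 2% | dose squared | +5.4 | +0.8 |
| 0% / 0% | dose squared | +5.5 | +0.6 |

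Differences are percentage points; Monte Carlo standard error is 0.2 to 0.3. An independent re-run gave the same signs and similar sizes. The Fast share was 49-58% under the table limit and 33-36% under the weekly limit. Mean steps, Fast v Other, in the 60%/20% row were 3.78 v 2.73 (table) and 3.54 v 3.12 (weekly). In the 5%/2% row they were 4.15 v 3.76 and 3.98 v 3.99. The link with escalation is thus weaker under the weekly limit, because the one-week doses come early.

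**The case against.** The best defence is that little rests on this table. It is descriptive and late-added, with no test or decision rule, and the main safety summaries do not use it. Dose-related safety is examined elsewhere: down-titration or discontinuation at the maximum dose (Core SAP 5.6.1), falls by dose at onset (Core SAP 5.6.2), plasma level against selected adverse events (Core SAP 5.1.2), and adverse events by dose at onset (Extension SAP 5.6.2). That stands and limits the importance of the point, although none of these isolates speed.

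It can also be said that the protocol is coherent: a planned schedule with a weekly floor, so that the permitted time is the floor. That is a natural reading, but the SAP does not adopt it in words. The derivation rules and table shells are in separate documents that were not available here and may settle it.

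A reader might go further and infer that fast titration will look safer than it is. One calculation seems to support this: with five steps, q = 0.2 and a 10% chance at each dose of an event that stops escalation, such events appear in 31% of Fast and 64% of Other. But that concerns only escalation-stopping events, whereas the planned table counts all TEAEs. It also includes events at 12 mg, where no escalation is left to stop; without them the figures are 23% v 60%. For any TEAE the sign reverses, as shown above.

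A reader might also infer that the weekly reading leaves Fast almost empty. The documents give no frequency of short holds, and at q = 0.2 about a third of children are Fast on that reading.

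**Conclusion.** The point holds in a limited form. The split is confounded by escalation and by early stopping, and its threshold is not defined in days. With speed having no effect, the crude difference in any TEAE ran from -7.9 to +5.5 percentage points across the assumed scenarios. The documents contain no rates that would fix its sign, so they do not support the claim that the table will flatter fast titration, or the opposite claim. The ambiguous limit causes misclassification and does not by itself favour either direction.

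That zero-step children can only be Other follows from the definition alone. That the chance of being Fast rises with each step needs only some chance of a short hold at each. The sizes depend on the assumed q, target doses, hazards and stopping rates. Because the table is descriptive, what is affected is its interpretation, not a trial decision. This is a cheap improvement.

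**What to change.** In Core SAP 5.6.2:

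- Assign each TEAE by the child's titration status at its onset, either time-updated or from a landmark, counting upward steps only, with exposure time in each status as the denominator.
- Show children who never completed an upward step in their own column, not in Other.
- Present the table by EIAED status or maximum dose, and amend the exemption in SAP Section 5 to match. Maximum dose is itself reached after baseline, so EIAED status is the cleaner split.
- State the number of days per dose, for each schedule column, used for classification.

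In the protocol, the weekly-interval text in 9.1.2.1 and 9.4.1 must be reconciled with the two-week holds in Tables 1 and 2, and the SAP should then cite the result. This review takes no view on which interval is right.

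Cost: SAP wording, one table shell, one clarifying sentence in the protocol and a little programming. Dosing dates and adverse event onset dates are already needed for other planned analyses. The downside is a sparser table.

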### **AEs of special Interest**

A listing of subjects with AEs related to suicidality, identified by relevant Standardized MedDRA Query (SMQ) terms, will be provided. TEAEs of special interest listed below will be summarized by SOC and PT. SMQs will be used to identify relevant terms for the following TEAEs.

- TEAEs suggestive of abuse potential
- TEAEs related to alertness and cognition
- TEAEs related to psychosis / psychotic disorders
- TEAEs related to hostility/aggression

- TEAEs related to status epilepticus/convulsions
- TEAEs related to lab abnormalities
- Cardiac and ECG TEAEs
- TEAEs related to rash

TEAEs related to rash will be identified by medical review. Falls will be summarized for the Pretreatment Phase and Follow-up Period and will be summarized by actual dose of onset for the Titration and Maintenance Periods.

